9.2. Implementation phase of the protocol

- The inclusion criteria for study subjects will be strictly followed;
- The randomization of the e-cigarette stores will be strictly carried out using random numbers.
- Two staff members will accompany the team to each surveyed metropolitan area and provide implementation assistance to simulated buyers and answers to their questions whenever needed.

9.3. Analysis phase of the protocol

Two analysts will conduct independent data cleaning and logical error correction of data (e.g., range checks for data values). Any discrepancies uncovered will be resolved by the principal investigators.

10. Ethics

10.1. Ethical approval and informed consent

According to previous literature²⁴⁻²⁷, this study does not involve human subject research or collect any private information. Prior to the study, the investigators will submit the protocol to the Institutional Review Board at Peking University, which may exempt this trial from ethical review.

Following prior research, this trial uses the mystery shopping approach, and all the study subjects (e-cigarette stores and cigarette stores) will not be informed that they will be enrolled in this trial.²⁴⁻²⁶

10.2. Legality

Purchase of e-cigarette products by adolescent buyers (age ≥ 18) is legal in China. This study does not involve the collection of private personal information from sellers.

10.3. Follow-up processing

For the purchased e-cigarette and cigarette products, some will be given to scientific research institutions for academic purposes, and others will be sent to tobacco control associations as samples for educational purposes.

11. Data processing and storage

The data will be collected through the self-developed instrument embedded in the Questionnaire Star platform (an App on smart phones), downloaded by the investigators at the end of the survey and saved on the principal investigator's computer located in the office. Statisticians will create the database in a timely manner, and the data will then be backed up and locked with passwords by investigators and research assistants after it has been thoroughly reviewed. To ensure data security, a non-permitted person cannot modify the data. All related analyses will be conducted on the principal investigator's computer. Staff who have access to the information of the trial subjects will sign confidentiality agreements. All the data in the study will be available to principal investigators, who have ultimate authority for the decision on data. The information shall not be disclosed to any third party (other than persons or institutions directly involved or required to know by law) without the prior consent of principal investigators. The investigators must take all appropriate precautions to avoid disclosing the information to third parties or the public by any staff or institutions.

12. Study Timeline

We plan to complete the preliminary recruitment of adolescents who will work as simulated buyers and data collectors, store sampling, and pilot survey from June 2023 to July 2023. In July 2023, we will train the simulated buyers and conduct the randomization of simulated buyers and e-cigarette stores. From July 2023 to September 2023, we will divide the data collectors into three teams and carry out the trial investigation. Data cleaning and analysis will be conducted after September 2023.

13. Role of funding source

This study is funded by the China Medical Board in the United States. The funder will have no role in the study design, data collection, analysis, interpretation, or writing of the paper.

14. Declaration of interests

There are no financial or other competing interests for the principal investigators in the overall trial or at each study site.

15. Reference

Lanzhou (Gansu Province)	Chengguan, Qilihe, Anning, Xigu, Honggu
Lhasa (Xizang Autonomous Region)	Chengguan, Duilongdeqing
Nanchang (Jiangxi Province)	Donghu, Xihu, Qingyunpu, Honggutan, Xinjian, Qingshanhu
Nanjing (Jiangsu Province)	Xuanwu, Qinhuai, Jianye, Gulou, Qixia, Yuhua
Nanning (Guangxi Autonomous Region)	Xingning, Qingxiu, Xixiangtang, Jiangnan, Liangqing, Yongning
Ningbo (Zhejiang Province)	Haishu, Jiangbei, Beilun, Zhenhai, Yinzhou, Fenghua
Qingdao (Shandong Province)	Shinan, Shibeい, Laoshan, Licang, Huangdao
Shanghai (Shanghai Municipality)	Huangpu, Xuhui, Changning, Jing'an, Putuo, Hongkou, Yangpu, Pudong New Area
Shenyang (Liaoning Province)	Heping, Shenhe, Dadong, Huanggu, Tiexi
Shenzhen (Guangdong Province)	Futian, Luohu, Nanshan, Yantian
Shijiazhuang (Hebei Province)	Changan, Qiaoxi, Xinhua, Yuhua

Taiyuan (Shanxi Province)	Xinghualing, Jiancaoping, Yingze, Wanbailin, Xiaodian, Jinyuan
Tianjin (Tianjin Municipality)	Heping, Hedong, Hexi, Nankai, Hebei, Hongqiao
Urumqi (Xinjiang Autonomous Region)	Tianshan, Shayibake, Xinshi
Wuhan (Hubei Province)	Jianghan, Wuchang, Jiang'an, Hongshan, Hanyang
Xiamen (Fujian Province)	Siming, Huli, Haicang, Jimei
Xi'an (Shaanxi Province)	Lianhu, Xincheng, Yanta, Beilin, Baqiao, Weiyang
Xining (Qinghai Province)	Chengdong, Chengzhong, Chengxi, Chengbei
Yinchuan (Ningxia Autonomous Region)	Xingqing, Xixia, Jinfeng
Zhengzhou (Henan Province)	Jinshui, Erqi, Guancheng Hui, Zhongyuan

Appendix 2 Communication script in the e-cigarette store

Soft script

When the simulated buyer, acting as a customer, communicates face-to-face with the seller in an e-cigarette store, the main information recorded includes: successful purchases of e-cigarette products, inquiries about age, requests to show ID cards, dissuasion from using e-cigarettes, price information, and marketing strategies (such as the store clerk adding you on WeChat). You can use the following conversational sentences to naturally gather the above information:

Other key points: advertising area, warning slogans, decorations, product types, flavor recommendations, information conveyed, and discounted prices.

Legal requirements: (record only)

- **Does the seller in the e-cigarette store ask about your age?**
- **Have you been asked by the seller to show your ID card?**

1. When you walk into the store or approach the counter, first glance at the wall to see if there is a tobacco license. Then look at the e-cigarette products, paying attention to any "No use by minors" warning signs and "Smoking or vaping is harmful to health" warning signs. Continue to pretend you are browsing the store.
2. Typically, the seller will notice you immediately and ask what you are looking for. You should respond with "I'm just browsing," "I'm here to learn about the products," or "My friend uses e-cigarettes, and I'm here to check them out."
3. The seller will likely ask if you have used e-cigarettes or smoked before. You should respond, "I have never used them before." At this point, some sellers may advise you not to buy or try them.

4. You should ask the seller, "Do you have any recommendations?" The seller will likely recommend a lighter flavor product and hand it to you. You then ask, "Is this detachable?" or "Can this be used continuously?" to determine the type of e-cigarettes sold in the store. While doing this, take the opportunity to look around to see if there are disposable e-cigarettes and open-system e-cigarettes, as well as whether protective cases and lanyards are sold at the counter.

5. During the ongoing product viewing phase, point to the various e-cigarette cartridges on the counter or shelf and ask the seller about their differences. Then further inquire, "Which ones sell well?" or "What do people often buy?" or "Which are popular?" Take note of the first and second flavors mentioned by the clerk. If the seller offers you a sample, be sure to refuse!

6. After learning about the popular flavors, express how popular e-cigarettes are around you by saying something like, "I have a few friends who use them," "I've seen many people using them," or "I've seen others using them several times while shopping." Use this to prompt the seller to explain why e-cigarettes are popular. They will generally actively market a positive image of e-cigarettes. Please note the content and order of what the seller says, taking down the first two to three points.

7. By asking "I've smelled someone using an e-cigarette with a sweet flavor, do you have that?", observe whether the seller tries to sell you flavored e-cigarettes, and note the flavor. Be careful not to mention words like "fruit" to avoid arousing the seller's suspicion. Pay attention to whether the seller mentions illegal products like "milk tea cups" and record them, but the decoy should not bring them up proactively.

8. Inquire about the prices of e-cigarettes, including the cigarette rod and cartridge. If the seller recommends Relx e-cigarettes, respond with, "That's a bit expensive, any discounts?" to record discount information. Then say, "I want to try first, do you have anything cheaper?" to express that it is still too expensive. Continue this until the seller explicitly replies that it is the cheapest product in the store. If the store only sells pod-based e-

cigarettes, say, "I can use my friend's cigarette rod" to purchase only the cartridge and not the rod. Disposable e-cigarettes are usually cheaper than pod-based ones, and if offered by the seller, you can purchase them.

9. When you pay, observe whether there are contact details (such as WeChat number, WeChat group code, phone number, etc.) on the counter. If the seller actively adds you on WeChat, they will likely also mention, "We offer online mailing services." If the seller does not actively mention online mailing, you should ask, "Why add WeChat?" and record the seller's reaction.

10. You should observe whether there are any "free trial" signs or disposable flavor filters placed in the store. Pay attention to whether the seller advises you against using e-cigarettes.

[figure not shown]
11. While you are in the store picking products or after making a purchase, take a moment to naturally browse the merchandise. Observe whether other items like tobacco, alcohol, or areca nuts are sold on the shelves, and whether toys and decorative ornaments are displayed.

Handling Special Situations:

- If a seller offers you to try an e-cigarette, they usually provide a disposable tool. Respond with, "This seems unsanitary, I won't use it... I'd rather buy a new one/I'd rather use my friend's."
- The seller might claim that the e-cigarette and cartridges are sold as a set, and that a friend's e-cigarette might not be compatible. You should insist on only buying the cartridges, "It's fine, I remember it's just like this one/... just buy a box of these."

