6.3. Other outcome measures

Other outcome measures primarily include:

- Illegal flavored products being sold

The simulated buyers will report if sellers mention that flavored (not allowed in China) e-cigarette products are available in the stores.

- Online contact

The simulated buyers will report if WeChat account information is publicly displayed for adding contacts.

- Delivery service offered

The simulated buyers will report if sellers mention that products ordered online can be delivered to them.

- Marketing claims

The simulated buyers will record the marketing claims of sellers to promote the products

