- WeChat (a mobile instant messaging software)
- QQ mobile (a mobile instant messaging software)
- Phone number
- Other _____
- No

39. Does the seller proactively provide online shopping services in an attempt to send e-cigarette products through social platforms? [Single Choice Question] * ----- If you were asked to add WeChat in the previous question, ask, "Why add WeChat?" If the seller says that he or she can send it to you online by adding WeChat, then select "Yes" for this question. Be sure to find a reason to refuse to add WeChat, such as replying, "No, I will buy it myself when I have time."

- Yes
- No

40. Is the contact information (including WeChat, phone number, etc.) publicly displayed in the store? [Single Choice Question] * ----- Usually, this is a small sign on the checkout counter, or it may be a brand WeChat group.

- Yes
- No

41. Do you (the simulated buyer) have any other notable observations that you would like to add? [Fill in the blanks] *

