## **Other Outcome Measures**

- Illegal flavored products being sold: The simulated buyer will report if the seller mentions that flavored (non-national-standard) e-cigarette products are available in the stores.
- Online contact: The simulated buyer will report if WeChat account information is publicly displayed for adding contacts.
- Delivery service offered: The simulated buyer will report if the seller mentions that products ordered online can be delivered.
- Marketing claims: The simulated buyer will record the marketing claims made by the seller to promote the products

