#### **2.3.4. Analysis of Other Outcomes**

Other outcomes, including illegal flavored products, online contact, and delivery service offered, will be analyzed in a similar way as the primary outcome. Chi-square tests will be used to detect statistical significance in differences between the two groups, and logistic regression models appropriate for the distribution of the binary outcomes with covariate adjustments will be employed. Similar national maps describing geographic variations will be generated as well. For marketing claims and strategies, we will further employ thematic framework analysis to qualitatively analyze and describe the marketing methods and tactics of e-cigarette stores.

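### Online contact is a standing store feature that attire cannot change, yet it is tested between arms as an outcome, and whether it is observed depends on how the visit goes

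*Protocol*

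**What the plan says.** Protocol 6.3 defines online contact this way: "The simulated buyers will report if WeChat account information is publicly displayed for adding contacts". SAP 2.2.1 has the same definition. The only questionnaire item on displayed contact details is Q40 in Protocol Appendix 4: "Is the contact information (including WeChat, phone number, etc.) publicly displayed in the store". It is answered Yes or No, with the guidance "Usually, this is a small sign on the checkout counter, or it may be a brand WeChat group".

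On analysis, SAP 2.3.4 states: "Other outcomes, including illegal flavored products, online contact, and delivery service offered, will be analyzed in a similar way as the primary outcome". It continues: "Chi-square tests will be used to detect statistical significance in differences between the two groups", with covariate-adjusted logistic regression in addition. Protocol 8.4 plans the same.

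On observation, step 9 of the script in Protocol Appendix 2 begins "When you pay, observe whether there are contact details". Q23 of the questionnaire sends any buyer who was asked to leave straight to submission, so Q40 is not reached. Protocol 8.7 analyses interior store features on available data only.

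**The concern.** A sign on the counter is there whatever the buyer wears, so the true attire effect on this item is zero. That is an inference from the definition, not a sentence in the documents, but it is a safe one. The SAP itself treats comparable displays (licence, age-of-sale warning, health warning) as store covariates in 2.2.2. The contact behaviours that attire could change are separate items: Q38, the seller offering to exchange contact details, and Q39, the seller offering online supply.

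The look is prompted at payment, and Protocol 2.1 expects uniforms to make a sale less likely. Protocol 7.1.4 confirms that the buyers who record the data know the attire. A between-arm test therefore has no real effect to find, but it can find a difference in who looked or in who was left in the data. A reader of the results table could take such a difference for a change in how retailers treat uniformed buyers.

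**Working it through.** **Inputs.** The plan gives no figure for online contact, so there is none to reproduce. From the documents: about 1,080 stores at 1:1, so 540 per arm; two-sided alpha 0.05; cluster size 4; intracluster correlation 0.5 (Protocol 8.6, SAP 1.4, set for the primary outcome). The documents give no display, purchase or asked-to-leave rates. All such rates below are assumptions.

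**Step 1. Follow each kind of visit to Q40.**

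| Visit | Prompted to look at step 9? | Q40 |
|---|---|---|
| Sale made | Yes | Answered |
| Age first checked when paying, sale refused | Yes; the Q23 note has the buyer continue | Answered |
| Refused mid-conversation, not asked to leave | No | Yes or No required; an unseen sign becomes No |
| Asked to leave | No | Skipped, so missing |

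The mix of these four kinds arises after randomisation, and the trial's hypothesis is that attire shifts it.

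**Step 2. Equal looking, nothing missing.** The true difference is 0, so a valid test rejects 5% of the time and every rejection is false. A chi-square test that ignores clustering rejects 2 × (1 − Φ(1.96/√DE)), where DE = 1 + (4 − 1) × ICC. At ICC 0.05, DE = 1.15 and the rate is 6.8%. At ICC 0.5, DE = 2.5 and the rate is 21.5%.

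**Step 3. Unequal looking.** This concerns the third row of the table only. Recorded difference = display rate × arm gap in the share of Q40 respondents not prompted to look × gap in detection.

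- Low: 0.40 × 0.20 × 0.35 = 0.028, or 2.8 points.
- High: 0.60 × 0.40 × 0.65 = 0.156, or 15.6 points.
- Middle: display 50% in both arms, purchase 50% (uniform) against 80% (casual), refused buyers detecting half as often. Uniform 0.5 × (0.50 + 0.50 × 0.5) = 37.5%; casual 0.5 × (0.80 + 0.20 × 0.5) = 45.0%. At 540 independent stores per arm, p < 0.05 occurs about 71% of the time.
- With purchase 70% against 80%: 42.5% against 45.0%, and p < 0.05 about 13% of the time.

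These figures use the purchase gap as the gap in not being prompted. That treats every non-purchase as a mid-conversation refusal that answered Q40. Asked-to-leave visits and refusals at payment do not belong there.

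**Step 4. Selective missingness.** Suppose looking is perfect but asked-to-leave visits are dropped: 20% in the uniform arm and 5% in the casual arm, all of the latter in stores that would also ask a uniformed buyer to leave.

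- Display 60% in stores that would not ask a uniformed buyer to leave, 20% in those that would. Uniform: 60.0%. Casual: (0.80 × 0.60 + 0.15 × 0.20)/0.95 = 0.51/0.95 = 53.7%. The truth in both arms is 0.80 × 0.60 + 0.20 × 0.20 = 52%. The uniform arm is 6.3 points higher and both arms overstate prevalence. The chance of p < 0.05 is about 50%.
- Swap the two display rates. Uniform: 20.0%. Casual: (0.80 × 0.20 + 0.15 × 0.60)/0.95 = 0.25/0.95 = 26.3%. The truth is 0.80 × 0.20 + 0.20 × 0.60 = 28%. The sign reverses and both arms understate.
- Equal display rates in the two kinds of store give no difference.

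Steps 3 and 4 can add or cancel.

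**The case against.** The strongest reply is that the questionnaire limits the problem. Buyers asked to leave do not record a false No, because they never see Q40. Buyers refused at payment are at the counter, where step 9 tells them to look. Only buyers refused mid-conversation remain, and the script is a soft one: they may approach the counter at step 1, check what is sold there at step 4, point to products on it at step 5 and browse at step 11. Q40 asks about the whole store, and field training requires more than 90% of objective items correct (Protocol 7.4.2). All of this stands, and it shrinks the unequal-looking part. It does not remove it, since no step before 9 tells the buyer to look for contact details, and it turns the asked-to-leave visits into a missing-data problem.

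A second reply is that this is one item outside the stated hypotheses, closest to a descriptive exploratory objective, and that store features are compared between arms descriptively anyway (Protocol 8.1, SAP 2.3.1). Nor does either document say that a difference would be reported as seller behaviour. That stands on severity. It does not justify listing a fixture among outcomes analysed like the primary one.

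**Conclusion.** The concern holds as a minor point. Attire cannot change displayed contact details, so apart from chance any arm difference in Q40 reflects unequal looking or selection after randomisation. This rests on the published definition; it would not apply to Q38.

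Three stronger readings are tempting, and the documents do not support them:

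- **Every refused buyer records a false No.** Q23 removes those asked to leave, and payment-stage refusals are prompted to look.
- **The uniform arm will be lower and prevalence understated.** Unequal looking pushes that way, but step 4 shows that missingness can push either way.
- **The expected bias is 2.8 to 15.6 points.** All three inputs are assumed, and the formula fits only buyers refused mid-conversation who did not look.

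The primary and secondary results are unaffected.

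**What to change.** - **Script (Protocol Appendix 2):** move the look for contact details from step 9 to the first scan in step 1, with the licence and warning signs.
- **Questionnaire (Protocol Appendix 4):** move Q40 ahead of Q23, beside Q15 to Q18, so that every buyer who enters records it. Moving the script line alone would not reach buyers asked to leave.
- **Analysis (Protocol 8.4 and SAP 2.3.4 together, so that they stay consistent):** report displayed contact as one overall prevalence and drop its between-arm test as an outcome, or keep that comparison only as a labelled negative-control check. If a seller-behaviour contact measure is wanted, use Q38, which is already collected.

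The cost is one script line, one reordered item with the matching training note, and one sentence in each document. What is lost is a test with no real effect to find. If fieldwork has already begun, the analysis change alone still applies, since the SAP is to be final only before database lock. The prevalence should then be described as recorded display among visits that reached Q40, with the number of asked-to-leave visits given by arm.

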Appendix 3 Pictures for models wearing school uniforms and casual attire

School uniform, male

School uniform, female

Casual attire, male

Casual attire, female

Appendix 4 Assessing tool

E-cigarette store survey questionnaire

Basic Information

1. Survey date [Fill in the blanks] *-----Click to confirm

2. Simulated buyer's name [Fill in the blank] *-----Fill in the name

3. City where you are located [Fill in the blanks] *-----Please fill in "Beijing" in the format, do not fill in "Beijing City"

4. Store ID: _____ [fill in the blank] *----- Each store corresponds to an ID. Note that there may be e-cigarette stores very close to each other in practice, and the store names might not be easily distinguishable. Please check carefully.

5. Location of store: (automatically fill the building location by the GIS function embedded in the Questionnaire Star) [Fill in the blank] *

6. The simulated buyer's attire today [single-choice question] *

- Student uniform
- Casual attire

Outside Store Observation

7. Is it possible to study this store? *[Single choice question]

- Yes;

○No, unable to locate the store based on the geographic information. You can follow the map navigation to the building and walk around the area to try to find it. If you still cannot find it, contact the study coordinator to add a new store;

○No, possible danger in surroundings was perceived, such as remote alleys with no pedestrians at all;

○No, store closed upon arrival, even though it was confirmed to be in business before.
Note that some unopened stores can be observed, such as in pictures 1 and 2 below;

○No, other reasons _____ * (Please skip to the end of the questionnaire and submit your answer sheet).

8. The type of stores is [single choice question] *

○Open stores in shopping malls -----based on whether the counter can be accessed from the pedestrian area;

○Enclosed stores in shopping malls;

- Convenience store or small supermarket on the street — not primarily selling e-cigarettes;

- E-cigarette store with independent stores on the street

- E-cigarette store under an office building ----- [please note the distinction from an e-cigarette store that is an independent store on the street];

○Other type _____ *

9. Are any of the following places near the e-cigarette store (look around and within sight)?

[Multiple choice questions] *----- [Look around twice and mentally count 5 or more stores]

- School
- Shopping mall entrance, stairs-----This refers to the e-cigarette retail store in the mall
- Trendy toy store
- Beverage shop
- Female-only stores such as nail salons and cosmetics stores
- Internet cafe
- Bar
- Video arcade

- Mobile phone store-----primarily sells mobile phone cases, data cables, and screen protectors.

Others (such as: large supermarkets, clothing stores) _____ (i.e. next to the entrance of large supermarkets)

None of the above

10. In which of the following ways does the exterior decoration of the store attract the attention of passers-by? [Multiple choice questions] *----Brand names or store names such as "RELX" do not count as advertising.

General print advertising (posters, banners, flyers, etc.)

Backlit or illuminated advertising----refers to advertising that features LED lighting, video, and short clips accompanied by dynamic or static text display. [Note: When not illuminated, it is considered standard printed advertising.]

Three-dimensional advertising, such as large fixtures — refers to large e-cigarette installations used in e-cigarette stores for product promotion or promotional activity displays, including large props, dolls, etc. (see the figure below).

Other _____

No advertising

11. Area of large billboards: [Fill in the blanks _____] *---- Note: Take the prescribed poster as the first figure below. There may be more than just e-cigarettes in the advertisements in the second figure below. If there are too many advertisements in the third figure below, fill in 10. [For Question #10 above, if "Others" or "No advertising" is chosen, please fill in 0 for Question #11.]

12. Are there any billboards with the following characteristics outside e-cigarette stores?

[Multiple choice questions] *

Use of celebrity endorsements

Scenic photos, such as mountains, rivers, trees, and blue sky

Contains images of cartoon characters or animals ---- on billboards

□ Price discounts or promotional activities----advertisements for price discounts or promotions often include phrases such as 'limited-time offer,' 'X% off,' 'price reduction,' 'buy and get xxx free,' 'grab a bargain,' or 'carnival season.' and so on.

□ Ads showing e-cigarette flavors, such as photos of fruit

□ Other _____

Depends on options 1, 2, 3, or 4 of Question #10.

13. From the perspective of pedestrians, is there a recognizable "No Use by Minors" sign [Single Choice Question] *----The following large warning signs or clearly visible signs that can be seen from the outside

Yes

No

In-store communication and records 1

14. Can you enter the store to observe and record? Please select one of the following [Single Choice Question] *

Yes

No, the e-cigarette store is not open (please skip to the end of the questionnaire and submit your answer sheet)

No, the seller is not in the store (please skip to the end of the questionnaire and submit your answer)

No, other _____ * (please skip to the end of the questionnaire and submit your answer sheet)

15. Is the tobacco retail license visible [Single choice question] *

Yes

No

16. Is there a "No use by minors" slogan in the store (excluding slogans on product packaging) [Single-choice question] *

Yes

No

17. Are there any of the following health warning signs in the store (excluding slogans on product packaging) [Single choice question] *

Yes, there is a "Smoking is harmful to health" sign

Yes, there is a "E-cigarettes are harmful to health" sign

Yes, both of the above exist

No

18. Are there children's toys, car models, figurines, and/or other decorations placed on the shelves or counters? [Note that these decorations need to be targeted at teenagers.] [Single Choice Question] *

Yes, specifically _____ *

No

19. Gender of the seller: (When there are multiple sellers, this question refers to the seller who communicates with the simulated buyer the most. The same applies to the questions below.)

Male

Female

20. Age of the seller (the simulated buyer needs to estimate) [Single-choice question] *

18-24 years old

25-29 years old

30-39 years old

>40 years old

21. Did the seller ask the simulated buyer if he or she was an adult? [Single Choice Question] * -----Questions such as "Are you an adult?" "Are you over 18?" "How old are you?" "Are you a student?" etc.

Yes

No

22. Did the seller ask to see the simulated buyer's ID? (If the seller requires you to fill in identity information on the system, please select Yes.) [Single Choice Question] *

Yes

No

23. Did the seller ask the simulated buyer to leave? (No sales communication) [Single Choice Question] * ----- If the seller does not check the age until the simulated buyer pays, the sales communication has been completed at this point. In this case, you should select "No" and continue to fill in the questionnaire.

○No

- Yes, the seller asked you (the simulated buyer) to leave without asking about their age. (Please skip to the end of the questionnaire and submit your answer.)
- Yes, the seller asked you (the simulated buyer) to leave after asking their age. (Please skip to the end of the questionnaire and submit your answer.)
- Yes, the seller asked you (the simulated buyer) to leave after knowing that he or she did not have an ID card. (Please skip to the end of the questionnaire and submit your answer.)

In-store communication and records 2

24. Does the e-cigarette store sell the following types of e-cigarettes and accessories
[Multiple choice questions] **

Disposable e-cigarettes ----- Disposable e-cigarettes refer to those e-cigarettes that cannot be disassembled, refilled, or changed by the user and are thrown away after use. They can also be rechargeable. For example, the seller might describe them to you as "rechargeable for 1,000 puffs."

Reloadable e-cigarettes and/or cartridges ----- Reloadable e-cigarettes usually consist of two parts: a cigarette rod and a cigarette cartridge. The cigarette rod can be recharged and reused, while the cigarette cartridge is thrown away after use.

Open e-cigarettes that the user refills with e-liquid himself or herself ----- The e-liquid tank of open e-cigarettes is open and refillable. It can be refilled 3-6 times for continued use. The atomizer has a long service life.

Auxiliary accessories for e-cigarettes, such as protective cases, lanyards, etc.

Other, _____

25. Other items sold in the e-cigarette stores: [Multiple choice questions] *

No products other than e-cigarettes are sold

Power bank rentals

Addictive substances, such as tobacco, alcohol, and betel nut

Other _____

26. Did the seller proactively dissuade the simulated buyer from trying e-cigarettes? [Single Choice Question] * ----- The seller will tell you (the simulated buyer) that e-cigarettes are harmful, addictive, impossible to quit, don't try them, etc., in an attempt to discourage you from buying them.

Yes

No

27. The most popular flavor recommended to you (the simulated buyer) by the seller is [fill in the blank] * ----- Ask the seller, "With so many varieties, what are the differences?" and then, "Which one sells better?"

28. The second most popular flavor recommended to you (the simulated buyer) by the seller is [fill in the blank] * ----- If the seller only recommended one flavor in the previous question, you can fill in "none" for this question.

29. Is there a "Free Trial" sign or disposable filters in the store [Single-choice question] * -----Pay attention to whether there are disposable filters at the cashier]

Yes

No

30. Did the seller proactively mention the free trial? [Single-choice question] * -----The seller had a higher chance of letting you (the simulated buyer) try it, and might even assemble the e-cigarette and hand it over to you.

Yes

No

31. Are illegal flavored e-cigarettes sold? [Single Choice Question] * ----- Usually, illegal flavored e-cigarettes are not placed on display, lack obvious warning slogans on the packaging, and the product may be labeled in English.

Yes

No

32. Does the e-cigarette store sell illegal e-cigarettes with the following flavors [Multiple choice questions] *

- Fruit flavor
- Candy flavor
- Food or drink flavors
- Mint flavor
- herbal vaporizer
- Other, _____
- None of the above

Question #32 depends on option 1 of Question #31.

33. Did the seller proactively mention illegal e-cigarette products such as "milk tea cups" and "Coke cans" [Single-choice question] *

- Yes
- No

34. Does the information delivered to you (the simulated buyer) by the seller include the following? (Select in order) * ----- Use "E-cigarettes are very popular recently..." to potentially guide the seller to describe the reasons for the popularity of e-cigarettes.

- None
- E-cigarettes are less harmful

- [] E-cigarettes can be used in more places
- [] E-cigarettes are easily accepted by people around them
- [] E-cigarettes have a variety of flavors
- [] E-cigarettes do not produce unpleasant odors
- [] Other, _____

35. Are e-cigarettes promoted in the following ways? [Multiple choice questions] * -----

Ask "Are there any promotions?"

- Price discounts (including coupons, limited-time activities, group purchase discounts, etc.)
- Free products
- Small gifts
- Membership activities, points rewards
- Others _____
- None of the above

36. The lowest price of e-cigarette products is: [Fill in the blanks] * ----- If the cheapest one is a disposable e-cigarette, buy it and fill in the price. If there are only reloadable e-cigarettes in the store, you need to fill in the sum of the prices of the cartridges and the cigarette rods.

37. Did you (the simulated buyer) successfully buy e-cigarettes [single-choice question] *

- Yes
- No

38. Did the seller take the initiative to add your (the simulated buyer's) contact information?

[Single Choice Question] * ----- Pay attention to whether the seller took the initiative; you (the simulated buyer) should not take the initiative to ask. Please be sure not to agree to add WeChat.

- WeChat (a mobile instant messaging software)
- QQ mobile (a mobile instant messaging software)
- Phone number
- Other _____
- No

39. Does the seller proactively provide online shopping services in an attempt to send e-cigarette products through social platforms? [Single Choice Question] * ----- If you were asked to add WeChat in the previous question, ask, "Why add WeChat?" If the seller says that he or she can send it to you online by adding WeChat, then select "Yes" for this question. Be sure to find a reason to refuse to add WeChat, such as replying, "No, I will buy it myself when I have time."

- Yes
- No

40. Is the contact information (including WeChat, phone number, etc.) publicly displayed in the store? [Single Choice Question] * ----- Usually, this is a small sign on the checkout counter, or it may be a brand WeChat group.

- Yes
- No

41. Do you (the simulated buyer) have any other notable observations that you would like to add? [Fill in the blanks] *

